**FORM: Application for Human Research**

NUMBER	FORM DATE	PAGE
F200		6 of 18

Clinical trial does not require registration (click above to see what studies qualify)

SECTION 3. PROJECT NARRATIVE**1) Background**

The primary objective of this study is to evaluate the efficacy of combining intense therapeutic ultrasound (ITU) with standard care for the treatment of chronic plantar fasciitis. A secondary objective is to evaluate the tolerability and safety of intense therapeutic ultrasound in the treatment of plantar fasciitis.

These objectives will be accomplished through the following specific aims:

Aim # 1: Compare patient reported outcomes of pain, function and level of activity for subjects treated with standard of care plus ITU (ITU group) to those treated with standard of care plus sham ITU (control group).

Aim # 2: Compare the changes in plantar fascia thickness in subjects treated with standard of care plus ITU to those treated with standard of care plus sham ITU.

Aim # 3: Evaluate the tolerability and safety of ITU for the treatment of chronic plantar fasciitis Chronic Plantar Fasciitis. Chronic plantar fasciitis (CPF) is a common cause of plantar heel pain that is a result of a degenerative process of the plantar fascia and its surrounding perifascial structures. It is the most common cause of heel pain, affecting 10% of the U.S. population, and one of the most common foot and ankle problems. One study showed that individuals with this disease scored significantly lower in general health-related quality of life in addition to foot specific quality of life (pain and function).

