The purpose of this study is to assess the effectiveness of ITU in the treatment of CPF by comparing pain, function, and change in plantar fascia thickness in subjects treated with ITU in addition to standard of care to subjects that are treated with standard of care alone. The primary outcome measure will be a computer adaptive questionnaire where pain, function and level of activity will be compared between the two groups. In addition, with the use of diagnostic ultrasound, plantar fascia thickness and presence or absence of hyper-echoic lesion will be compared between the two groups. Finally, the safety and tolerability of ITU will be monitored through the course of the study. It is hypothesized that patients receiving ITU in addition to standard of care will have a more rapid resolution of their pain, faster return to activities, and a greater decrease in plantar fascia thickening on ultrasound as compared to those only receiving standard of care.

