"We are seeking adults with chronic heel pain. Have you had chronic heel pain? Chronic heel pain is pain which has been present for at least 3 months and may be the result of plantar fasciitis. Have you had heel pain for the last 3 months? It may be the result of plantar fasciitis. Plantar Fasciitis is a painful, inflammatory condition occurring where the plantar fascia attaches to the calcaneus (heel bone). The most common symptoms are 1) pain with the first few steps in the morning, 2) pain at the beginning of an activity which improves as the plantar fascia is stretched during the activity, 3) pain and stiffness with prolonged standing, and 4) pain at the end of the day. The standard treatment of Chronic Plantar Fasciitis consists of stretching, anti-inflammatory medications (NSAIDS), and heel cups. Despite these treatments, 5% - 20% of patients will still have symptoms at 1 year! Participate in a study to determine the effectiveness of Intense Therapeutic Ultrasound for the treatment of Chronic Plantar Fasciitis. What is Intense Therapeutic Ultrasound? Intense Therapeutic Ultrasound (ITU) is a noninvasive method of healing tissues with sound waves. ITU promotes collagen generation and is FDA approved for the non-surgical lifting of the brow. What is the purpose of this study? The purpose of this study is to determine if intense ultrasound can promote healing of plantar fasciitis. This study will determine the effectiveness of ITU in speeding the healing of plantar fasciitis. The time required

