Interested individuals who contact the laboratory will have the logistics of the study explained and be referred to the clinic for diagnosis and treatment of heel pain. All patients diagnosed with plantar fasciitis by participating physicians will be contacted by the research team to discuss the details associated with participation. We would like to obtain a temporary deferment of authorization to obtain contact information from the electronic medical record for those individuals who are initially identified in the clinics by participating physicians. Additionally, we would like permission to provide the consent and authorization forms and other information by e/mail should this be conducive to obtaining informed consent. The mailing is for informational purposes only to allow the subject more time to consider participation in the study. The informed consent process will be completed in person. Both English and Spanish versions of the consent forms will be utilized, although the Spanish consent form will be submitted as a modification once the English version is approved. Finally, we would like to provide a map and information sheet to assist participation in the study (see attachments).

7) Procedures involved in the Human Research

After obtaining informed consent and authorization from the subject, study personnel will verify the screening of participants utilizing the inclusion/exclusion criteria and collect the following information- age, gender, height, weight, activity level, pain level, and physical exam findings including x-rays - which will be recorded on the data abstraction sheet (see attachment). The activities strictly associated with the research are the assignment to a study group (Control or ITU), the administration of patient reported outcome measures (questionnaires), and therapeutic and/or diagnostic ultrasound (Table 1). Additionally, adverse events will be recorded at each visit (see attachment). Treatment tolerability will be prior to, immediately after, and at 2 days post-treatment.

Standard of care is integrated into both arms of the investigation and includes a structured physical examination, the use of an NSAIDs for 3 weeks (Naprosyn 500 mg po bid or Ibuprofen 800 mg po tid taken with meals), viscoelastic heel cups for 12 weeks, and supervised physical therapy with home exercise program for 6 weeks. These components are described below-

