Diagnostic Ultrasound (Aim 2). Diagnostic ultrasound will be utilized to compare the changes in plantar fascia thickness that occurs over time in subjects treated with standard care to those treated with ITU plus standard of care. Diagnostic ultrasound imaging will be performed with an FDA approved ultrasound scanner (Spark® System, Ardent Sound, Inc. – Mesa, AZ, see Appendix 6 of proposal) using a coupling gel (Polysonic®, Parker Laboratories, Inc., Fairfield, NJ, see Appendix 7 of the attached proposal) by a trained sonographer or physician. The subject will be positioned prone on an exam table with the feet over the edge of the table. The plantar fascia of the affected and contralateral feet will be imaged. The width and depth of the fascia as well as the size and location of a hyperechoic lesion, when present, will be recorded using both long and short axis imaging. Change in plantar fascia thickness relative to the baseline measurement will be calculated. Decreased thickness of 0.8 mm or greater will be considered clinically significant as these changes have been shown to correlate with decreased pain and increased mobility.

Experimental Treatment: Intense Therapeutic Ultrasound (ITU). Subjects in the ITU group will receive standard treatment plus two treatments (at week 0 and week 2) of ITU to the affected plantar fascia (Table 1 in red). ITU treatment will be performed using a GEN II system (Guided Therapy Systems, Mesa, AZ). (Please see Appendix 5 of the Protocol.) We are seeking classification as a non-significant risk (NSR) device. (Please see the attached NSR statement.) Trained study personnel will conduct the treatments. The treatment session will last 15 – 20 minutes. During this time the subjects will be required to lay prone position on an exam table with their feet hanging over the end of the table. An average energy up to 5 joules / thermal zone will be administered to the symptomatic Plantar Fascia in a linear pattern along the Plantar Fascia (Figure 1) with up to 50 lines. Each line will include individual thermal zones, less than 1 mm³ in volume, centered at 10 – 13 mm depth, and approximately 2 mm apart.

[figure not shown]

Figure 1: The treatment site located around the insertion of the plantar fascia onto the posterior process of the calcaneus

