## Statistical Approach

- Pain Reduction:

Pain level at the plantar fascia was self-reported by subjects at pre-treatment (used as baseline measurement) and again at each follow-up - 4, 8, 12, and 26 weeks - after initial treatment. The pain scale subjects used to identify their level of pain was a 10-point pain scale range, where 0 = no pain, 1 = slight pain through 10 which equates to the patient's worst imaginable pain. The goal for all subjects in the treatment group was to reduce pain by at least 25%. Pain scores reported at follow-up timepoints were compared to baseline score for each subject to determine if the goal was met by dividing the difference in the follow-up and baseline pain score by the baseline pain score. The percentage of subjects that met the pain reduction goal was calculated at each timepoint for both control/sham-treated and treatment groups by dividing the number of subjects that achieved the pain reduction goal at each timepoint by the total number of patients that gave a pain score for that time point.

- Plantar Fascia Hypoechoic Lesion Size:

A large proportion of patients suffering from chronic plantar fasciitis present with hypoechoic lesions in or around the proximal plantar fascia, as viewed by diagnostic ultrasound imaging[7].

Hypoechoic lesions were imaged and volumes were calculated at the baseline visit and each follow-up visit by measuring the inferior-to-superior and posterior-to-anterior radii in the long axis and the medial-to-lateral radius of the transverse axis and applying the following formula for the volume of an ellipse:

$$\text{Volume} = (4/3)\pi \cdot r_1 \cdot r_2 \cdot r_3$$

With  $r_1$ ,  $r_2$ , and  $r_3$  representing the three radii detailed above. Changes to lesion volumes were recorded at each follow-up timepoint and compared to baseline by dividing the volume of the lesion at that timepoint with the volume of the same lesion at pre-treatment baseline.

- Foot Function Index Score Reduction:

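### No stated analysis validly answers Aim 2: the SAP text has no plantar fascia thickness analysis and tests lesion volume only against baseline, and the protocol's thickness comparison uses paired t tests

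*SAP*

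**What the plan says.** **Protocol.** Aim 2 (Section 3, 1) Background) is to "Compare the changes in plantar fascia thickness in subjects treated with standard of care plus ITU" with those on standard care plus sham. The Lay Summary (Section 3, 2) states the hypothesis as "a greater decrease in plantar fascia thickening on ultrasound as compared to those only receiving standard of care". It also plans that "plantar fascia thickness and presence or absence of hyper-echoic lesion will be compared between the two groups". Under Diagnostic Ultrasound (Aim 2) in Section 3, 7), the protocol says "Change in plantar fascia thickness relative to the baseline measurement will be calculated" and adds "Decreased thickness of 0.8 mm or greater will be considered clinically significant". The Statistical analysis paragraph of the same section plans a comparison of mean thickness between the two groups before and after treatment, and names paired t tests as the method.

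**SAP.** Statistical Approach covers three outcomes: the percentage of subjects reaching a 25% pain reduction, lesion volume, and the Foot Function Index pain score. On imaging it says only "Hypoechoic lesions were imaged and volumes were calculated at the baseline visit and each follow-up visit", with each follow-up volume divided by the same lesion's baseline volume. Statistical Calculations gives one kind of test, Student t-tests of baseline against follow-up, for self-reported and lesion size measurements, at a significance level of 0.05. Neither fascia thickness nor the 0.8 mm threshold appears, and no between-arm estimate or test is stated for lesion volume.

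**The concern.** Aim 2 asks whether thickness falls more with ITU than with sham. An analyst who followed the SAP text would produce no thickness result at all. For lesion volume, the result would be a test of whether it changed over time. An analyst who went back to the protocol would find the right outcome and the right contrast, attached to a test for paired observations. Subjects in the ITU and sham arms are different people and are not matched.

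The randomised comparison is what separates ITU from everything else the subjects receive. The protocol says "Standard of care is integrated into both arms of the investigation", and that care includes NSAIDs, heel cups and physical therapy. A significant change from baseline in the ITU arm could reflect those treatments, natural course or measurement drift, and so could be read as an imaging effect of ITU when there is none.

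**Working it through.** **Passages side by side**

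| Element | Protocol | SAP text |
|---|---|---|
| Outcome for Aim 2 | Change in fascia thickness | Not mentioned |
| Contrast | ITU versus sham | For lesion volume, baseline versus follow-up only |
| Threshold | Decrease of 0.8 mm or more | Not mentioned |
| Test | Paired t tests | Student t-tests against baseline |
| Lesion outcome | Hyper-echoic; presence or absence compared between groups; size recorded | Hypoechoic; volume as a ratio to baseline |

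No cell pairs the Aim 2 outcome with a valid test of the Aim 2 contrast. The documents derive no figure on this point: the target of 50 is given without a power, SD or effect size, so there is nothing to reproduce.

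**How far a within-arm test can mislead (illustration)**

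Inputs from the documents:
- target enrolment of 50 (Section 3, 5) Study Population)
- 1:1 allocation (Section 3, 7) Randomization and Blinding), so 50 / 2 = 25 per arm if the arms are equal
- significance level 0.05

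Assumptions:
- the test is two-sided, paired and run within the ITU arm (the SAP says only Student t-tests)
- ITU adds nothing, and both arms change by the same amount d, in units of the SD of individual change
- d runs from 0.1 to 0.8, because the documents give no value

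The SAP's imaging test is on lesion volume, so the n that matters is the number with a baseline lesion. The protocol Background reports hyper-echoic lesions in 68% to 84% of patients. If that range applied to the SAP's lesion and all 50 subjects were imaged, 50 × 0.68 = 34 to 50 × 0.84 = 42 would have one, or 17 to 21 per arm.

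Formula: the probability of significance is P(|T| > t crit), where T is noncentral t with n − 1 degrees of freedom and noncentrality d × √n. The critical values are 2.120 (n = 17), 2.086 (n = 21) and 2.064 (n = 25).

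| d | n = 17 | n = 21 | n = 25 |
|---|---|---|---|
| 0.1 | 7% | 7% | 8% |
| 0.2 | 12% | 14% | 16% |
| 0.3 | 21% | 26% | 30% |
| 0.5 | 49% | 59% | 67% |
| 0.8 | 87% | 94% | 97% |

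For example, at d = 0.5 and n = 25 the noncentrality is 0.5 × 5 = 2.5 and the probability is 0.670.

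A between-arm t-test on change stays at 5% throughout, because the true difference between arms is zero. A simulation of 40,000 runs with 25 per arm gave 0.050, 0.050 and 0.049 for the between-arm test at d = 0.3, 0.5 and 0.8, and 0.303, 0.671 and 0.971 for the within-arm test.

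**The case against.** **The protocol already plans the thickness comparison, and the SAP does not withdraw it.** This stands in part. A reader might infer that thickness was dropped or replaced by lesion volume. The documents do not show that. The SAP is silent, and the point covers only the SAP text available. But silence leaves the protocol's paired t tests as the only stated method, and they do not make the comparison.

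**The illustration measures the general weakness of within-arm tests, and its upper end depends on the assumptions.** This stands. With 25 per arm the figures overstate what applies to lesion volume, where 17 to 21 per arm is the better guess, and at a shared change of 0.1 to 0.2 SD the probability is only about 7% to 16%. A reader might also take the recruitment text ("Despite these treatments, 5% - 20% of patients will still have symptoms at 1 year") as evidence of imaging improvement under standard care. It concerns symptoms at 1 year, whereas Table 1 ends imaging at week 12, and entry requires at least three months without improvement. The argument from design needs none of these numbers.

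**The lesion terms may differ only in wording.** This may be so. Both documents use long-axis and short-axis or transverse measurements and describe a lesion found in most or many patients, which fits a single lesion type. A reader might infer that a different lesion was analysed; the documents do not settle it. They need reconciling, no more.

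**Two further inferences fail.** The volume ratio is not ill-defined, because the SAP divides by the same lesion's baseline volume and so implicitly limits it to subjects who had one; only the number analysed is missing. The SAP's follow-up weeks (4, 8, 12 and 26) appear only in its pain paragraph, so no mismatch with the imaging visits is shown.

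**Conclusion.** The point holds on the text. Aim 2 is a between-arm question about thickness, and no analysis stated in either document validly answers it: the SAP text omits the outcome, and the protocol names a test that does not fit the contrast. The SAP's lesion-volume tests do not fill the gap, since they address change over time in another measure.

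The possible size of the error is wide and rests on assumed values. With no ITU effect, a within-arm test would be significant with probability about 7% to 87% at n = 17 and about 8% to 97% at n = 25, against 5% between arms. These are not estimates for this trial.

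This should be corrected, but it does not touch the primary outcome: the Lay Summary makes a questionnaire the primary measure, and thickness is additional to it.

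**What to change.** In the SAP:

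1. Make the between-arm comparison of change in plantar fascia thickness the Aim 2 analysis, using an independent-groups method. Adjusting for baseline thickness (for example by ANCOVA) is preferable, since that measurement is already planned; an unadjusted two-sample comparison would be the minimum.
2. Record the replacement of the protocol's paired t test for thickness as a documented change.
3. Compare lesion presence or absence between arms, as the Lay Summary plans.
4. Report lesion volume between arms only as supplementary, in subjects with a baseline lesion, stating the quantity tested and the number analysed per arm and visit.
5. Reconcile hyper-echoic in the protocol with hypoechoic in the SAP.

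The SAP is written in the past tense, so anything the protocol did not plan, such as baseline adjustment or a between-arm analysis of lesion volume, should be labelled post hoc. The thickness comparison and lesion presence are already planned and need no such label.

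The cost is a little more analysis work. No new measurement is needed if imaging followed the Diagnostic Ultrasound section.

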**FORM: Application for Human Research**

NUMBER	FORM DATE	PAGE
F200		8 of 18

3) Setting of the Human Research

The PI is an assistant professor in the Department of Orthopaedic Surgery and surgeon with the University of Arizona Health Network. Subjects will be recruited from the outpatient clinic of Drs. [name] (PI) and [name]. The age, gender, height, weight, activity level, pain level, and physical exam findings of patients will be obtained directly from the subject, the subject's medical record, or from direct examination and then recorded in a password protected excel file. The online survey can be completed from any computer available to the subject. Intense therapeutic ultrasound and diagnostic ultrasound will be administered in the Human Movements Biomechanics Lab (BRL B101).

4) Resources available to conduct the Human Research

Equipment for intense therapeutic ultrasound will be provided by [name] and [name] from Guided Therapy Systems. The equipment for measuring height and weight will be in the orthopedic clinic. Personnel available to conduct the study include 2 surgeons, 1 clinical research coordinator, 2 sonographers, 1 medical student, and 2 undergraduate assistants. These individuals will be available to recruit and consent patients, coordinate and conduct the study, analyze the data, and produce a manuscript.

5) Study Population

Male and female adults (18 years or older) with plantar heel pain and point tenderness near the medial calcaneal insertion of the plantar fascia for at least three months without improvement will be considered for inclusion into the study. Subjects with diabetes, bilateral plantar heel pain, current systemic or local infection, previous foot surgeries, other foot/ankle pathologies (inflammatory arthritis, gout, neurologic disorders, connective tissue disorders and malignancy), contraindications to the use of NSAIDs, and pregnancy will be excluded. The target enrollment of this pilot study is 50 participants.

6) Recruitment Methods and Consenting Process

Subjects will be recruited utilizing public media, list serves, community organizations, and via referral. Please see the attachments to this application for an electronic media and brochure representations of the advertisements to be utilized. We would like to select from the following wording to produce recruitment materials -

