Assessment of Safety and Tolerability (Aim 3). Subject self-assessments of treatment tolerability will be conducted immediately after, two days after (phone survey) and two weeks after treatment using a 10-point visual analog scale (VAS, see Appendix 1-C). The subject will be asked to report their current level of pain and the maximum level of pain experienced over the last two days. The VAS is the standard for assessing pain for both clinical and research purposes. Recording of adverse events will take place at all visits (see adverse event reporting form Appendix 4 in the protocol). Adverse events and serious adverse events will be monitored throughout the study. A treatment will not be administered if there is residual pain/discomfort experienced by the subject from the previous treatment.

Statistical analysis. Data will be assessed for variance homogeneity and normality. FFI-P, PFCAT, and FAAM scores before and after intervention will be compared between the two groups using a paired t-test. Additionally, the mean thickness of the plantar fascia will be compared between the two groups before and after treatment and significance determined utilizing paired t tests. P<0.05 is considered to be statistically significant.

8) Risks to subjects

Exposure to ITU may produce short-term sensations which may cause discomfort and mild erythema for up to a few hours following the exposure. No detrimental side effects have been reported in previous clinical trials investigating similar devices in which ultrasound energy was applied to the neck and face. Additionally, the ITU in this investigation will utilize lower power parameters than those reported for these similar devices. We are seeking classification of the GEN II system (Guided

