If an injury occurs, medical care is available. No funds are available to cover compensation for any injury incurred as a result of participation in this investigation.

15) Withdrawal of subjects

Subjects may withdraw from the study at any time either in person, in writing, or by telephone. Subjects withdraw by contacting either [name] or the project lead. Abrupt withdrawal

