**FORM: Application for Human Research**

NUMBER	FORM DATE	PAGE
F200		15 of 18

presents no risk. Should subjects fail to comply with instructions given to them, they may be withdrawn from the study.

16) Sharing of results with subjects

The results of the study will not be shared with subjects.

17) Information management

N/A

18) Drugs, Devices, and Gases

Equipment for intense therapeutic ultrasound will be provided by [name] and [name] from Guided Therapy Systems and operated by trained sonographers.

- a) Name of drug/device: GEN II
- b) FDA approval status of the drug/device: We are seeking classification as a Non-Significant Risk (NSR) Device with the following reasons-
 - (a) GEN II will not be utilized nor is intended to be utilized as an implant. Additionally, the device does not present a potential for serious risk to the health, safety, or welfare of a subject.
 - (b) GEN II is not purported or represented to be for a use in supporting or sustaining human life and does not present a potential for serious risk to the health, safety, or welfare of a subject.
 - (c) The GEN II device is not of substantial importance in diagnosing, curing, mitigating, or treating disease, or otherwise preventing impairment of human health and does not present a potential for serious risk to the health, safety, or welfare of a subject.
 - (d) The GEN II does not otherwise present a potential for serious risk to the health, safety, or welfare of a subject.
- c) The GEN II will be controlled by the PI and/or representatives of the sponsor, Guided Therapy Systems:
 - i) The device will be stored in the PI's laboratory located in the Department of Orthopaedic Surgery, Biological Research Buildings, Building B Room 101 or in possession of GTS representatives.
 - ii) The site is sufficiently secure to protect the equipment.
 - iii) The storage condition for the equipment is not of concern beyond normal sheltered conditions.
 - iv) The GEN II device does not require stringent control and tracking of utilization.

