In addition to the 11-point VAS pain scale, patients self-reported answers to questions from the Foot Function Index (FFI) pain subscale questionnaire, which has been standardized in a number of PF-focused publications [8-10]. Scores range from 0-90, with 0 indicating no pain and 90 indicating the worst pain imaginable in a variety of daily activities involving use of the plantar fascia. Self-reported scores were taken at baseline and each follow-up timepoint. The average score for each timepoint were calculated, and follow-up averages were compared to baseline to calculated the percentage reduction in score.

- Statistical Calculations

Student T-tests were utilized to determine statistically significant differences between baseline and subsequent follow-up measurements for self-reported and lesion size measurements. The level of significance ( $\alpha$ ) was set to 0.05.

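### The SAP does not say that the FFI percentage reduction uses the same subjects at baseline and follow-up; if scores are missing, it can rise or fall with nobody changing

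*SAP*

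**What the plan says.** The SAP (Statistical Approach, Foot Function Index Score Reduction) defines the FFI result as a comparison of averages: "The average score for each timepoint were calculated, and follow-up averages were compared to baseline to calculated the percentage reduction in score". It gives no rule for a missed FFI score and does not say whose baseline enters the baseline average.

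The other two results in the same SAP section are tied to the individual. For pain: "Pain scores reported at follow-up timepoints were compared to baseline score for each subject". For lesions, the follow-up volume is divided by "the volume of the same lesion at pre-treatment baseline". The pain responder rate also allows for missing scores, because its denominator is set "by the total number of patients that gave a pain score for that time point".

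The protocol (Section 3, item 15) says "Subjects may withdraw from the study at any time" and also "Should subjects fail to comply with instructions given to them, they may be withdrawn from the study". Under item 10, when a participant leaves, the identifying records are destroyed but the study data are kept.

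On testing, the protocol (Section 3, item 7, Statistical analysis) says that FFI-P and other "scores before and after intervention will be compared between the two groups using a paired t-test". The SAP names only Student t-tests of baseline against follow-up and does not say whether they are paired.

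**The concern.** A percentage built from two averages measures change only if both averages describe the same people. If a subject's baseline score is counted and the follow-up score is missing, the follow-up average moves because the group has changed. Losing high scorers lowers it and looks like improvement; losing low scorers, such as recovered subjects who stop answering, raises it and hides improvement.

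The FFI percentage is one of only three results the SAP defines, and the arms are small. A reader given the percentage without the number of scores behind it could not tell whether such a shift had occurred, or in which direction.

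**Working it through.** **Inputs from the documents.** Target enrolment is 50 (Protocol Section 3, item 5) with 1:1 allocation (item 7), so 50 / 2 = about 25 per arm. The FFI range is 0-90 (SAP). The documents give no FFI mean, SD, attrition rate or result, so there is no plan figure to reproduce.

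**Assumptions.** Baseline mean 50; SD 15 (range 10 to 20); 2, 5 or 8 follow-up scores missing of 25.

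**Formula as written.** Reduction = 1 - (mean follow-up of those who answered) / (mean baseline of all).

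**Hand check, nobody changes.** Take 20 subjects at 40 and 5 at 80.
- Baseline mean = (20×40 + 5×80) / 25 = 48.
- The five at 80 are missing: follow-up mean = 40, and 1 - 40/48 = 16.7% apparent reduction.
- Five at 40 are missing instead: follow-up mean = (15×40 + 5×80) / 20 = 50, and 1 - 50/48 = -4.2%, an apparent worsening.
- Same subjects in both averages: 40/40 or 50/50, so exactly 0%.

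The 16.7% is an extreme pattern, with every high scorer leaving. It shows the mechanism, not a likely size.

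**Simulation, nobody changes (40,000 arms of 25).** Leavers are drawn without replacement with weight exp(b·z), where z = (score - 50)/15. A weaker link is b = 0.5 (weight ×1.65 per SD); a strong link is b = 1 (×2.7 per SD). The table gives the mean apparent reduction.

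| Loss | 2 lost | 5 lost | 8 lost |
|---|---|---|---|
| Random | 0% | 0% | 0% |
| Weaker link | ±1.2% | ±3.2% | ±5.3% |
| Strong link | ±2.3% | ±5.7% | ±9.3% |

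The sign is plus if high scorers leave and minus if low scorers leave. With five lost at random, 90% of single arms lie within about -5 to +5%. For SD 10 to 20 and five lost, the weaker link gives 2.1 to 4.3% and the strong link 3.8 to 7.6%. With the same subjects in both averages, every cell is 0%.

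**Simulation, true fall 50 to 35.** The true reduction is 1 - 35/50 = 30%. Five are lost, the link is strong, and the baseline to follow-up correlation is assumed to be 0.6.

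| Who leaves | As written | Same subjects |
|---|---|---|
| High baseline | 33.4% | 29.4% |
| Low baseline | 26.6% | 30.5% |
| High follow-up score | 35.6% | 33.3% |
| Low follow-up score | 24.3% | 26.7% |
| Least improved | 32.5% | 34.2% |
| Most improved | 27.4% | 25.5% |

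Using the same subjects is closer to 30% in the first four rows and further from it in the last two. A baseline-adjusted estimate returns about 30% when loss follows the baseline score. In the last two rows it lands close to the same-subject figure, so it does not repair them.

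**The case against.** The strongest reply is that this is an inference from silence. The SAP never says that different subjects were averaged, and no document shows a missing FFI score. The sign that missing scores were expected comes from a different instrument (the pain scale) and from standard withdrawal wording. Remote completion should limit missing scores: "The online survey can be completed from any computer available to the subject". If every score was obtained, or only completers were averaged, the problem disappears. All of that stands, and it limits the point to an undefined calculation. It does not supply the missing definition.

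Second, the percentage is descriptive and inference rests on the t-tests. If these were paired, as the protocol says for FFI-P, they used subjects with both scores and the p-values are not affected by the mismatch. That also stands, with the reservation that the SAP does not say paired. The percentage could still rest on a different set of subjects from its p-value.

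Third, the sizes depend on an assumed mean, SD, number lost and strength of link. With the weaker link and five lost, the average shift of 3.2% is inside the random-loss range for one arm. This is fair.

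Stronger readings that a reader might infer, and that the documents do not support:
- That the FFI result is biased in favour of ITU. No attrition is given, and the shift can go either way or be zero.
- That an ITU-versus-sham contrast of FFI percentages is distorted. The SAP defines no such contrast, and for the FFI it does not say that averages are taken by arm.
- That the pain responder rate has the same fault. Its denominator rule is stated.
- That restricting to the same subjects gives an unbiased answer. The last two rows of the second table show otherwise.

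**Conclusion.** The point holds as a gap in definition with a measurable consequence if scores are missing. The literal FFI calculation does not guarantee that the two averages cover the same people. Under the assumptions above, with five of 25 lost, the shift in a single arm averages about 3 to 6% in either direction for score-related loss and 0% for random loss.

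It should be corrected, but it does not undermine the trial. The FFI is not the primary outcome named in the protocol's Lay Summary (Section 3, item 2), the study is a pilot, and a paired test would be unaffected. Confidence is medium for two reasons: the mismatch is inferred from what the SAP leaves out, and the separate protocol listed among the attachments (Protocol Section 4, item 9) was not available and may contain a missing-data rule.

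**What to change.** 1. State that FFI change at each visit is computed within subjects who have both a baseline score and a score at that visit, and that any percentage uses those same subjects' baseline average.
2. Report the number of FFI scores per arm and visit, including subjects with no follow-up score.
3. Compare ITU with sham, which is the protocol's Aim 1, by a baseline-adjusted repeated-measures model using every randomised subject with at least one follow-up score. Label it post hoc if data have already been seen, which the SAP's past tense suggests is possible.

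**Cost.** Some SAP wording, one table and a modest analysis of data already collected, with no new visits.

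**Downside.** The model assumes data missing at random. When loss depends on the change itself, neither step removes the bias, and both can be further from the truth than the figure as written. With a true 30%, the same-subject figure is about 34% against 32.5% as written if the least improved leave, and about 25.5% against 27.4% if the most improved leave. That is why the counts in step 2 are needed beside any percentage. If no scores are missing, the percentage is unchanged and the counts will show it.
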